#### **Conclusion**

GS-5245 as a perpetrator: GS-5245 is not an inhibitor of CYP3A (as observed with MDZ) or a clinically relevant inhibitor of OATP1B1/1B3 (as observed with PIT).

GS-5245 as a victim: There was no effect of P-gp inhibition (as observed with coadministration of GS-5245 with ritonavir) on plasma exposures of GS-441524. There was no clinically significant effect of increased gastric pH (as observed with FAM) on the plasma exposures of GS-441524; thus, GS-5245 may be coadministered with ARAs including antacids, other histamine H2-receptor antagonists, as well as proton-pump inhibitors.

## **1.3.** Rationale for This Study

COVID-19 is a cause of an ongoing global pandemic with IV RDV being the first antiviral treatment approved by regulatory agencies in the US {VEKLURY 2022a, Veklury 2022b}, Europe {VEKLURY 2022a, Veklury 2022b} and multiple countries. More convenient options are needed for early intervention in the nonhospitalized COVID-19 population.

The oral bioavailability of RDV is low based on nonclinical studies (< 1% in cynomolgus monkey) and unlikely to generate adequate human systemic exposure of RDV to drive antiviral activity against SARS-CoV-2 in the lung {Mackman 2021}. GS-5245 is an ester prodrug of the parent nucleoside of RDV, GS-441524. Following oral administration, GS-5245 is projected to deliver high systemic levels of GS-441524 and adequate formation of the active nucleoside triphosphate metabolite, GS-443902, in tissues where SARS-CoV-2 replicates. Administration of oral GS-5245 therefore represents a promising approach for the treatment of COVID-19.

This Phase 3 superiority study will evaluate GS-5245 compared with placebo in participants who are at high risk for disease progression but who:

- Cannot take existing therapies that are authorized or approved (ie, nirmatrelvir/ritonavir, molnupiravir, ensitrelvir, IV RDV, monoclonal antibodies, or any other locally authorized or approved direct-acting therapy against SARS-CoV-2) because of medical contraindications or clinical concerns from the investigator.
- Continue to lack access to existing therapies that are authorized or approved after exhausting all locally available means in attempts to make these therapies accessible for participants.

Participants who do not have medical or clinical contraindications to authorized or approved therapies, and also have concurrent access to and ability to easily receive nirmatrelvir/ritonavir, molnupiravir, ensitrelvir, IV RDV, monoclonal antibodies, or any other locally authorized or approved direct-acting therapy against SARS-CoV-2, are excluded from enrollment and should be treated with these agents outside this clinical study.

## 1.4. Rationale for Dose Selection of GS-5245

The proposed dose for evaluation in this Phase 3 study is GS-5245 350 mg **twice daily** for 5 days. This dose was selected based on the totality of available clinical and nonclinical data and with careful consideration of the overall risk-benefit profile.

GS-5245 safety and PK were evaluated in a Phase 1 single and multiple ascending dose study (GS-US-611-6248) in healthy participants. Single GS-5245 doses up to 1600 mg and multiple doses of GS-5245 500 mg twice daily and GS-5245 900 mg once daily for 5 days were generally safe and well tolerated (most AEs were Grade 1 in severity). A graded laboratory abnormality of decreased  $CL_{cr}$  was observed across all cohorts, although there was a disproportionately higher number of participants with decreased  $CL_{cr}$  at the highest dose evaluated (single GS-5245 1600 mg dose).

Following oral administration of GS-5245, the GS-441524 metabolite was the only circulating species. The plasma half-life of this metabolite was approximately 6 hours, supporting twice daily dosing. The twice daily dosing regimen also provided higher daily exposure (AUC0-24h), higher  $C_{tau}$  concentrations, and lower  $C_{max}$  as compared with once daily dosing (Section 1.2.1.1.2).

GS-5245 builds on the already proven mechanism of action of RDV that is inhibition of SARS-CoV-2 RNA polymerase by the active triphosphate metabolite, GS-443902. The major metabolic pathways leading to formation of the GS-443902 metabolite are different between RDV and GS-5245. For GS-5245, the major metabolic pathway is through phosphorylation of the GS-441524 metabolite by cellular kinases, a pathway that is believed to play a minor role in activation of RDV to GS-443902 metabolite. In order to overcome the less efficient conversion to GS-443902, the levels of GS-441524 need to be approximately 14-fold higher, as compared with what is observed after RDV, in order to result in the similar levels of intracellular active metabolite. Robust intracellular formation of active metabolite was observed in the GS-US-611-6248 clinical study in PBMCs (eg, GS-5245 500 mg administered twice daily achieved GS-443902 levels comparable with IV RDV on Day 1 and exceeded those on later days by approximately 4-fold). The intracellular formation of GS-443902 was dose-proportional and significant accumulation was observed following twice daily dosing (approximately 6-fold accumulation by Day 5).

GS-5245 showed therapeutic efficacy in multiple SARS-CoV-2 animal models (ie, mouse, ferret and African green monkeys [AGMs]). Administration of GS-5245 to SARS-CoV-2-infected mice (10 mg/kg twice daily; AUC0-24h = 10,500 h•ng/mL), ferrets (20 mg/kg once daily; AUC0-24h = 28,500 h•ng/mL) and AGM (60 mg/kg once daily; AUC0-24h = 25,700 h•ng/mL) for 5 days resulted in a significant reduction of clinical signs of respiratory disease, infectious virus titers in lungs, and genomic RNA compared with vehicle-treated animals. Similarly, in the AGM model, IV delivery of parent nucleoside (20 mg/kg once daily; AUC0-24h = 42,800 h•ng/mL) and oral administration of GS-621763, a tri-isobutyryl ester tool prodrug of GS-441524 (60 mg/kg once daily; AUC0-24h = 18,200 h•ng/mL); (120 mg/kg once daily; AUC0-24h = 36,400 h•ng/mL) significantly reduced SARS-CoV-2 levels in the lower airways, as early as 1 to 2 days after infusion {Cox 2021, Pitts 2022}.

GS-5245 350 mg twice daily dose was selected for evaluation in this Phase 3 study for the treatment of COVID-19 in participants at high risk for disease progression; this dosing regimen should provide systemic exposures of GS-441524 (predicted AUC0-24h = 30,100 h•ng/mL) associated with efficacy in the SARS-CoV-2 animal models. Moreover, this dosing regimen allows for GS-441524 concentrations over the dosing interval to be predominantly maintained above the effective concentration (EC50) needed for SARS-CoV-2 viral inhibition in normal human bronchial epithelia cells (EC50 = 713 ng/mL). This dosing regimen also provides a substantial exposure (Cmax) margin relative to the 1600 mg dose (approximately 2- to 3-fold) where potential drug-related effects on CLcr were observed. Additionally, plasma exposures of GS-441524 in participants with mild renal impairment are expected to be within the range of those observed in the GS-5245 500 mg twice daily cohort in Study GS-US-611-6248. This is supported by the RDV renal impairment study (GS-US-540-9015), where mild renal impairment

resulted in approximately 19% increase in  $AUC_{inf}$  and approximately 6.7% increase in  $C_{max}$  of this metabolite.

## 1.4.1. Participants with Compensated Cirrhosis

Hepatic metabolism and/or excretion is expected to be minimal (< 20%) in the elimination of GS-5245 or the plasma metabolite GS-441524, and thus, hepatic impairment is unlikely to alter the PK sufficiently to warrant dose adjustment of GS-5245. In the first-in-human study (GS-US-611-6248), GS-5245 was shown to be extensively hydrolyzed to GS-441524 metabolite presystemically with no detectable concentrations of the prodrug itself in plasma. Most of the absorbed dose (assuming 40% to 60% absorption) was excreted in urine over 24 hours postdose as GS-441524 metabolite (see Section 1.2.1.1.3.1).

The proposed biotransformation and elimination pathways of GS-5245 and GS-441524 are also supported by nonclinical data, including the radiolabeled absorption, distribution, metabolism, and excretion study in rats (Study AD-611-2021; Study AD-611-2022). Renal excretion was the major route of elimination of GS-441524 from the systemic circulation in these studies. Additional data from portal vein-cannulated dog and cynomolgus monkey (Study AD-611-2016; AD-611-2017) suggest GS-5245 metabolism occurs primarily in the gut. Only transient and low levels of intact GS-5245 were observed in the portal vein. This is consistent with the in vitro intestinal instability of GS-5245 (Study AD-611-2024).

Together, clinical and nonclinical data indicate minimal liver involvement in metabolism of GS-5245 following oral administration and support the use of the full clinical dose in participants with compensated cirrhosis in this Phase 3 study.

#### 1.5. Risk/Benefit Assessment for the Study

Potential risks of a participant's study involvement include unknown AEs, general risks associated with laboratory blood draws, and the associated pain and discomfort of phlebotomy.

Strategies to mitigate these risks include close monitoring of participants' clinical statuses, laboratory values, and AEs. Parameters for discontinuation of the study drug due to AEs will be clearly defined and closely followed.

Participants in this study will receive either GS-5245 or placebo. Conducting a fully powered Phase 3 safety and efficacy study allows for the most rapid assessment of the potential of GS-5245 to provide a treatment option for participants with COVID-19. Participant safety will be further protected by the oversight of the data monitoring committee (DMC) that will evaluate safety data when the first 200 participants reach Day 29 or prematurely discontinue from the study and when 50% of planned participants complete the Day 29 assessment or prematurely discontinue from the study, or 50% of expected primary endpoint events occur, whichever happens earlier.

Participants who are willing and able to take an authorized or approved therapy for COVID-19 will be excluded from the study. Before approving the study, institutional review boards (IRBs)/institutional ethics committees (IECs) will evaluate whether in accordance with local authorizations, approvals, treatment guidelines, and availability, there are potentially eligible participants who cannot or will not be able to access alternative care.

An infectious disease pandemic may pose additional risks to study drug availability, the study visit schedule, and adherence to protocol-specified safety monitoring or laboratory assessments. Refer to Appendix 11.2 for further details on the risks and risk mitigation strategy.

Considering the above, the benefit -risk balance for this study is considered positive.

#### 1.6. Compliance

This study will be conducted in compliance with this protocol and in accordance with the ethical principles that have their origin in the Declaration of Helsinki and that are consistent with International Council for Harmonisation (ICH) Good Clinical Practice (GCP) and applicable regulatory requirements.

## 2. OBJECTIVES AND ENDPOINTS

 
To evaluate the efficacy of GS-5245 the rate of COVID-19–related hospit all-cause death
 
Secondary Objective(s)
 
To evaluate the safety and tolerabilit administered in nonhospitalized part COVID-19
 
To evaluate the efficacy of GS-5245 all-cause hospitalization
 
	alization or       or all-cause death by Day 29         Secondary Endpoint(s)         y of GS-5245       Incidence of treatment-emergent AEs and laboratory abnormalities         Incidence of SAEs and AEs leading to study drug discontinuation

 
To evaluate the safety and tolerabilit administered in nonhospitalized part COVID-19
 
To evaluate the efficacy of GS-5245 all-cause hospitalization
 
	
 
y of GS-5245
 
Incidence of treatment-emergent AEs and laboratory abnormalities
 
Incidence of SAEs and AEs leading to study drug discontinuation
 

 
administered in nonhospitalized part COVID-19
 
To evaluate the efficacy of GS-5245 all-cause hospitalization
 
	
 
icipants with laboratory abnormalities
 
Incidence of SAEs and AEs leading to study drug discontinuation
 

all-cause hospitalization	in reducing • Proportion of participants with all-cause
	hospitalization by Day 29
• To evaluate the efficacy of GS-5245 COVID-19–related medically attend (MAVs) or all-cause death	
• To evaluate the efficacy of GS-5245 COVID-19–related MAVs	in reducing • Proportion of participants with COVID-19– related MAVs by Day 29
• To evaluate the efficacy of GS-5245 all-cause death	in reducing • Proportion of participants with all-cause death by Day 29
• To evaluate the efficacy of GS-5245 the duration and severity of COVID-	
• To evaluate the antiviral activity of C SARS-CoV-2 nasal swab viral load a	
• To evaluate the plasma PK of GS-44 (metabolite of GS-5245)	
 
Plasma concentrations and PK parameters AUCtau, Ctau, and Cmax of GS-441524, as available
 

CCI	

## **3. STUDY DESIGN**

#### 3.1. Study Design Overview

This Phase 3 study will be a randomized, double-blind, placebo-controlled study comparing the safety and efficacy of oral GS-5245 with placebo in nonhospitalized participants with COVID-19 who are at high risk of progression to hospitalization.

After screening procedures, eligible participants may be randomized in a 1:1 ratio to receive treatment with GS-5245 or placebo.

Randomization will be stratified by duration of symptoms at enrollment ( $\leq 3$  days versus > 3 days) and vaccination status (ever versus never).

An overview of the study design is shown in Figure 1.

#### **3.2. Duration of Intervention**

Duration of dosing is 5 days.

#### **3.3. Protocol-Specific Discontinuation Criteria**

#### **3.3.1.** Criteria for Early Discontinuation for the Individual Participants

3.3.1.1. Criteria for Early Discontinuation for the Individual Participants From Study Intervention

Study drug will be discontinued in the following instances:

- An SAE suspected to be related to study drug.
- Any  $\geq$  Grade 3 clinically significant AE suspected to be related to study drug.
- An AE, or worsening of clinical condition requiring clinical intervention, that would, in the judgment of the investigator, affect assessments of clinical status to a significant degree.
- Any ≥ Grade 3 clinically significant laboratory abnormality (if confirmed by repeat testing) suspected to be related to study drug.
   Except if baseline or on-treatment CLcr < 50 mL/min or eGFR < 50 mL/min/1.73m^2, then study drug is to be discontinued without confirmation by repeat testing and irrespective of relatedness.
- Unacceptable toxicity, as defined in Section 7.7, or toxicity that, in the judgment of the investigator, compromises the ability to continue study-specific procedures or is considered not to be in the participant's best interest.
- Baseline or on-treatment alanine aminotransferase (ALT)  $\geq$  5 × ULN.

- Baseline or on-treatment bilirubin  $\ge 2 \times ULN$  ( $\ge 3 \times ULN$  for participants with Gilbert's syndrome).
- Participant request to discontinue for any reason.
- Participant noncompliance.
- Pregnancy (refer to Appendix 11.3).
- Discontinuation of the study by sponsor.

If a participant discontinues study drug, every attempt should be made to keep the participant in the study and continue to perform the required study-related follow-up and procedures.

3.3.1.2. Criteria for Early Discontinuation for the Individual Participant From the Study

The participant will be discontinued from the study regardless of whether treatment is ongoing in the following instances:

- Withdrawal of consent.
- Death.

## **3.3.2.** Criteria for Early Discontinuation of the Study

The study will be discontinued in the following instances:

• Discontinuation of the study at the request of Gilead Sciences (Gilead) or a regulatory agency, IRB, or IEC.

## **3.3.3.** Loss to Follow-up

Should the participant fail to attend a scheduled protocol-specific visit, sites will need to make at least 3 attempts by a combination of telephone, email, or mail to contact the participant. Sites must document all attempts to contact the participant. If a participant does not respond within 5 days after the third contact, the participant will be considered lost to follow-up and no additional contact will be required.

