#### 8.5. Efficacy Analysis

#### 8.5.1. Primary Analysis

The primary endpoint is the proportion of COVID-19–related hospitalization or all-cause death by Day 29. COVID-19–related hospitalization is defined as  $\geq$  24 hours of acute care for a reason related to COVID-19, in a hospital or similar acute care facility, including emergency rooms or temporary facilities instituted to address medical needs of those with COVID-19. This includes specialized acute medical care units within an assisted living facility or nursing home. This does not include hospitalization for the purposes of public health and/or clinical study execution. The date and duration of hospital admission, and primary reason for hospitalization (including if the hospitalization is related to COVID-19) will be recorded.

The primary endpoint will be analyzed using a Cox proportional hazards model with the stratification factors (duration of symptoms and vaccination status) as covariates. The hazard ratio and 95% CI will be provided. Handling of intercurrent events is defined in Section 8.5.3.

The number and percentage of participants with COVID-19–related hospitalization or all-cause death by Day 29, and reasons for missing data will be summarized.

The FAS will be used for the primary efficacy endpoint analysis.

Sensitivity analyses may be conducted using the following alternative approaches for the primary endpoint.

- Missing hospitalization status will be imputed using multiple imputation assuming missing at random.
- A participant with missing hospitalization status will be imputed as the participant was hospitalized.

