3.8. Analysis Visit Windows

3.8.1. Definition of Study Day

Study day will be calculated from the first dosing date of study drug and derived as follows:

- For assessment dates on or after the first dosing date: Assessment Date First Dosing Date + 1
- For days prior to the first dose: Assessment Date First Dosing Date

Therefore, Study Day 1 is the day of first dose of study drug administration.

Last Dose Date is defined as the maximum, nonmissing, nonzero dose end date of treatment recorded on the Study Drug Administration eCRF form with "Study Drug Permanently Withdrawn" box checked for participants who prematurely discontinued or completed study drug according to the Study Drug Completion eCRF. Refer to Section 4.2 for missing date imputation, if necessary.

Last Study Date is the latest of the study drug start dates and end dates, the in-person or virtual visit dates, the vital sign collection dates, the questionnaire collection dates, the laboratory collection dates, and the death date (if applicable, for participants who died during the study, the death date will be the Last Study Date. For participants who died after completing the study or after prematurely discontinuing the study, the death date will not be considered for the Last Study Date).

Baseline value is defined as the last value obtained on or prior to the first dose date unless otherwise specified (see Section 3.8.3).

3.8.2. **Analysis Visit Windows**

Participant visits might not occur on protocol-specified days. Therefore, for the purpose of analysis, observations will be assigned to analysis windows.

The analysis windows for vital signs are provided in Table 3-1.

Table 3-1.	Analysis Visit V	Vindows for	Vital Signs

		Visit Window Study Day	
Analysis Visit	Nominal Study Day	Lower Limit	Upper Limit
Baseline	1	(none)	1
Day 3	3	2	4*
Day 5	5	4*	7
Day 10	10	8	12
Day 15	15	13	22
Day 29	29	23	34

If the nominal visit is a scheduled visit and the assessment is done on Day 4 (ie, Study Day = 4), assign to Day 3 or Day 5 analysis window based on the nominal visit label. If the nominal visit is an unscheduled visit or early discontinuation visit on Day 4, assign to Day 3 analysis window.

The analysis windows for SARS-CoV-2 mid-turbinate nasal swab are provided in Table 3-2.

		Visit Window Study Day	
Analysis Visit	Nominal Study Day	Lower Limit	Upper Limit
Baseline	1	(none)	1
Day 3	3	2	4*
Day 5	5	4*	7
Day 10	10	8	12
Day 15	15	13	22

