6. EFFICACY ANALYSES

6.1. Primary Efficacy Endpoint

6.1.1. Definition of the Primary Efficacy Endpoint

The primary endpoint of the study is the proportion of COVID-19–related hospitalization or all-cause death by Day 29. The endpoint will be derived by combining the available all-cause death and COVID-19–related hospitalization reported by the site.

COVID-19–related hospitalization is defined as \geq 24 hours of acute care for a reason related to COVID-19, in a hospital or similar acute care facility, including emergency rooms or temporary facilities instituted to address medical needs of those with COVID-19. This includes specialized acute medical care units within an assisted living facility or nursing home. This does not include hospitalization for the purposes of public health and/or clinical study execution. The date and duration of hospital admission, and primary reason for hospitalization (including if the hospitalization is related to COVID-19) will be recorded.

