6.1.3. Primary Analysis of the Primary Efficacy Endpoint

The FAPS will be used for the primary efficacy endpoint analysis.

The hazard ratio of COVID-19–related hospitalization or all-cause death by Day 29 between the 2 treatment groups will be estimated using a Cox proportional hazards model with the stratification factors (duration of symptoms and vaccination status) as covariates. The hazard ratio, p-value, 95% confidence interval (CI) for the hazard ratio from the Cox model, and proportion of COVID-19-related hospitalization or all-cause death at Day 29 from the Kaplan-Meier estimate will be provided. In addition, the p-value from stratified log rank test will be provided. If 5 events or fewer across both treatment groups are observed within 1 or more stratum, the primary endpoint will be evaluated in the same analysis described above without using the corresponding stratification factor(s) as covariates.

If a participant prematurely discontinues from the study prior to Day 29 and prior to COVID-19-related hospitalization and is alive by Day 29, or the hospitalization status is missing, the participant is censored at the Last Study Date or Day 29, whichever is earlier. If a participant prematurely discontinues from the study prior to Day 29 and prior to COVID-19-related hospitalization and then dies on or prior to Day 29, then date of the death and status will be used for the primary analysis for this participant. If a participant has a COVID-19–related

hospitalization first and then dies, then date of the COVID-19–related hospitalization and status will be used for the primary analysis for this participant. If a participant has a non COVID-19-related hospitalization first and then dies without experiencing a COVID-19-related hospitalization, then date of the death and status will be used for the primary analysis for this participant. Handling of intercurrent events is defined in Section 6.4.

The number and percentage of participants with COVID-19–related hospitalization or all-cause death by Day 29 will be summarized.

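### The loss-to-follow-up rule lets sites stop contact well before Day 29 without checking hospital or vital status, and the SAP then censors those participants with no sensitivity analysis left

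*Protocol*

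**What the plan says.** Protocol 3.3.3 starts the process at a single missed visit: "Should the participant fail to attend a scheduled protocol-specific visit, sites will need to make at least 3 attempts by a combination of telephone, email,". Post is the third channel named. The site must document every attempt. After 5 days with no response to the third contact, "the participant will be considered lost to follow-up and no additional contact will be required". The section sets no spacing between attempts and no earliest study day. It names no one to contact other than the participant.

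The endpoint runs to a fixed day. Protocol 8.5.1: "The primary endpoint is the proportion of COVID-19–related hospitalization or all-cause death by Day 29". SAP 6.1.1 states where events come from: "The endpoint will be derived by combining the available all-cause death and COVID-19–related hospitalization reported by the site".

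For a participant who leaves early without a recorded event, "or the hospitalization status is missing, the participant is censored at the Last Study Date or Day 29, whichever is earlier" (SAP 6.1.3). The same section counts a later death when it is known, for a participant who discontinues early: "then dies on or prior to Day 29, then date of the death and status will be used for the primary analysis for this participant". The Last Study Date in SAP 3.8.1 is the latest of several dates, including study drug and visit dates, "the vital sign collection dates, the questionnaire collection dates, the laboratory collection dates, and the death date".

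Protocol 8.5.1 offered two optional sensitivity analyses for missing hospitalization status: multiple imputation, and counting missing as hospitalized. SAP 6.5 says they will not be done.

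**The concern.** A participant who is in hospital, or has died, is one who may not answer a telephone, email or letter. The rule allows follow-up to end because of that silence, so leaving the risk set can be a consequence of the primary event. The Cox model and the Kaplan-Meier estimate both treat censoring as unrelated to the event.

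The rule also sits badly with the estimand. SAP Table 6-1 lists loss to follow-up among the reasons for stopping treatment and handles it by treatment policy, which needs the outcome to be observed. Protocol 3.3.3 removes the duty to obtain it.

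The stake is a primary comparison resting on very few events, with no remaining planned analysis that would show whether missing status affects the result.

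**Working it through.** **1. How early follow-up can end.** Visit windows are in Protocol Table 1. No spacing between attempts is set, so all three can fall on the last day of the window; the 5-day wait is then added.

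| Missed visit | Window closes | + 5 days | Days left to Day 29 |
|---|---|---|---|
| Day 3 (± 1) | Day 4 | Day 9 | 20 |
| Day 5 (± 1) | Day 6 | Day 11 | 18 |
| Day 10 (± 2) | Day 12 | Day 17 | 12 |
| Day 15 (± 2) | Day 17 | Day 22 | 7 |

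Spreading the attempts over another day moves the first row to about Day 10. Every row ends before Day 29.

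**2. The plan's own power.** Inputs from Protocol 8.9 and SAP 1.3: 2300 participants randomized 1:1, placebo rate 2%, ratio 0.25, two-sided 0.05. Expected events: 1150 × 0.02 + 1150 × 0.005 = 23 + 5.75 = 28.75.

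- Two proportions: 90.0% (1151 per arm needed for 90%).
- Freedman: Φ(√28.75 × 0.75/1.25 − 1.96) = Φ(1.257) = 89.6%.
- Schoenfeld: Φ(√28.75 × |ln 0.25|/2 − 1.96) = Φ(1.757) = 96.1%.
- Simulated binomial counts x0 (placebo) and x1 (active), d = x0 + x1, rejecting when (x0 − x1)/√d > 1.96: 93%.

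These bracket the stated figures (over 90% in the protocol, approximately 90% in the SAP).

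**3. Events unseen in equal proportion in both arms.** The documents give no loss rate, so the fractions are assumptions.

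| Fraction unseen | Events seen | Simulated | Freedman | Schoenfeld |
|---|---|---|---|---|
| 0 | 28.75 | 93% | 89.6% | 96.1% |
| 10% | 25.88 | 90% | 86.3% | 94.1% |
| 20% | 23.0 | 86% | 82.1% | 91.4% |

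The ratio of rates does not move: (0.005 × 0.9)/(0.02 × 0.9) = 0.25, and likewise at 20%.

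One way to reach such fractions: if a share l of participants is lost, with r times the event risk of the others, they hold l·r/(1 − l + l·r) of all events. With l = 2% and r = 3 this is 0.06/1.04 = 5.8%; with l = 5% and r = 5 it is 0.25/1.20 = 20.8%. This is an upper limit, because some of those events would still become known.

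**4. How few unseen events matter.** This is a one-sided stress test, not a prediction. Take the rounded expected counts, 23 placebo and 6 active among 1150 per arm: the two-proportion p is 0.0015. Six unseen active-arm events (about 0.5% of that arm) give p = 0.061. Enrollment stopped below 50% (SAP 2.3). At 575 per arm the design rates give 575 × 0.025 = 14.4 events. Illustrated as 12 against 3, p = 0.019; two unseen active-arm events give p = 0.087.

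**5. The censoring date.** Table 1 collects medically attended visit (MAV) information at baseline, Days 3, 5, 10, 15 and 29, and early discontinuation. Every scheduled laboratory and vital-sign assessment after screening falls on one of those visits. The symptom diary is completed daily through Day 15, including days when no MAV status is collected. A diary date can therefore set the Last Study Date later than the last status check. Adjacent scheduled visits up to Day 15 are at most 5 nominal days apart; the gap grows if a participant misses more than one visit but keeps filling in the diary.

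**The case against.** Contact does not stop at once. Three documented attempts by a combination of methods and a 5-day wait come first, and the rule sets a minimum without forbidding more. There are other routes to an event. Table 1 asks for MAV information through Day 29. Hospitalization and death are serious adverse events, reportable throughout the study (Protocol 7.1.2, 7.3.3). Hospital records are source data (3.5), and serious events are reconciled with the safety database (SAP 7.1.4). All of this stands, but each route depends on the site learning of the event, and the gap concerns participants the site no longer has to contact. The instruction to make every attempt to keep people in the study (Protocol 3.3.1.1, 6.4) covers those who stop study drug.

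Four stronger readings are tempting, and the documents support none of them.

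- A reader might infer that the hazard ratio is pulled toward 1 because placebo has more events to lose. Equal proportional loss leaves it at 0.25. Attenuation needs a larger fraction lost on placebo, and nothing in the documents points to that.
- A reader might infer that every post-exit death is missed. A death by Day 29 that becomes known is counted.
- A reader might infer that the lost are counted as event-free to Day 29. They leave the risk set at the censoring date.
- A reader might infer that laboratory and vital-sign dates distort the censoring date. Scheduled ones coincide with MAV collection.

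**Conclusion.** The concern holds as a defect in a stated rule. Protocol 3.3.3 permits close-out up to about 20 days before the endpoint window ends with no status check. SAP 6.1.3 censors the result, and SAP 6.5 removes the analyses that would have probed it. The censoring can be informative; the documents do not show that it was.

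The size is conditional on assumed loss. Equal loss of 10% or 20% of events costs about 3 or 7 percentage points of simulated power at 2300, with no effect on the hazard ratio. Unequal loss biases the ratio in a direction the documents do not fix. Power at 2300 does not describe the trial as run: with fewer than half randomized, and a lower-than-expected event rate given as the reason for stopping (SAP 2.3), individual missed events weigh more. The diary effect on the censoring date is a secondary matter of a few days for most participants.

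**What to change.** 1. **Protocol 3.3.3.** Do not class anyone as lost before the Day 29 (+ 5 days) window closes. Retry contact at each remaining visit day. Before classing as lost, check alternate contacts, the treating physician or hospital, and death records, where consent and law allow. Enrollment closed on 06 October 2023, so new consent wording cannot help participants already enrolled; this item mainly serves later studies using the same template.
2. **Before database finalization.** Make one such status check for each participant recorded as lost, within existing consent and local law, and count any event found by Day 29.
3. **SAP 3.8.1 and 6.1.3.** Censor the hospitalization and MAV endpoints at the last date on which MAV or hospitalization status was collected. Known deaths by Day 29 stay as they are.
4. **SAP 6.5.** Reinstate the protocol's two missing-status sensitivity analyses. Under SAP 1, changes after SAP finalization are documented in the study report.

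Cost: a few calls or record checks per lost participant, slightly earlier censoring dates for some, and a little more analysis work. Existing consent may not permit every check, so item 2 may be incomplete; item 4 shows how much the remaining gaps matter.
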